5.3 Subject Population for Analysis

Data analysis will be performed in accordance with the intention to treat principle. If a violation of randomization occurs, all patients will be analyzed according to the original allocation.

The following information will be prospectively collected and reported:

- All-randomized population: Any subject randomized into the study, regardless of whether they receive the intervention.
- Protocol-compliant population: Any subject who was randomized and received both the study intervention and received the required protocol processing.

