3. STUDY DESIGN

3.1 General Design

Prospective, multi-centre, parallel-arm randomized controlled equivalence trial. Eligible patients will be randomized to either mucopexy without Doppler guided artery ligation or mucopexy with doppler guided hemorroidal artery ligation.

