3.2.1 Primary

[figure not shown]
Primary aim of the Hamlet trial is to demonstrate that mucopexy without DGHAL for grade III haemorrhoids have equivalent recurrence rate at 1 year follow up of DGHAL with mucopexy procedure

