3.5 Participating Institution and Surgeons

This multicenter trial is opened to the contribution of surgeons across Europe in order to achieve the required number of patient recruitment in the shortest period.

- All surgeons must have prior experience in the treatment of hemorrhoids with DGHAL and mucopexy.
- All participating institutions must have IRB (Institutional Review Board)/Ethics Committee approval in order to enroll patients in the trial.
- Recruitment of Centers will be by direct invitation or spontaneous proposal of Coloproctology Units interested in the study.
- Surgeons involved MUST have no potential conflict of interests in the procedure

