5. STATISTICAL ANALYSIS

5.1 Sample Size Determination:

A sample size calculation shows that 100 subjects per arm will suffice for accepting of the equivalent hypothesis with power of 0.8 and a type I error probability of 0.05, an equivalent limit of 15% and expected percentage of success in both control and experimental group of 90% (sample size calculated with R).

5.2 Statistical Methods:

Results will be expressed as either mean and standard deviation (SD) or frequency (percentage). Between-group comparisons will be performed using Student's t-test (normally distributed data) or Mann-WhitneyU test (skew data) for continuous variables or Chi-square test for categorical variables. All hypotheses will two-tails with p < 0.05 considered as statistically significant.

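### In a declared equivalence trial, section 5.3 names intention-to-treat by original allocation as the only basis of analysis and gives the protocol-compliant population no role in the equivalence conclusion

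*Protocol*

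**What the plan says.** Protocol section 3.1 describes the study as a "Prospective, multi-centre, parallel-arm randomized controlled equivalence trial". Section 3.2.1 sets the aim of showing that "mucopexy without DGHAL for grade III haemorrhoids have equivalent recurrence rate at 1 year follow up of DGHAL with mucopexy procedure". Section 5.1 plans 100 subjects per arm with power 0.8 and type I error 0.05, using "an equivalent limit of 15% and expected percentage of success in both control and experimental group of 90" percent. Section 5.2 adds "All hypotheses will two-tails with p < 0.05 considered as statistically significant". Neither 5.1 nor 5.2 mentions an analysis population.

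Section 5.3 does. It states "Data analysis will be performed in accordance with the intention to treat principle", and then "If a violation of randomization occurs, all patients will be analyzed according to the original allocation". It goes on to define an all-randomized population and a protocol-compliant one, the latter being "Any subject who was randomized and received both the study intervention and received the required protocol processing". The only use given for these two populations is that the information will be collected and reported. No sentence says that the equivalence comparison is made in the protocol-compliant set, that the two sets should agree, or what follows if they do not. The protocol processing that the definition requires is not specified.

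**The concern.** In a superiority trial, analysing crossed-over patients as allocated works against the claim, because mixing the treatments shrinks the observed difference. In an equivalence trial the same shrinkage works for the claim. Section 2 shows that equal effectiveness is what this trial hopes to conclude, so the rule in 5.3 errs in the favourable direction whenever patients receive the other procedure.

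At stake is the chance of declaring the two operations equivalent when 1-year recurrence truly differs by the full 15-point limit. The population that would help to show whether dilution has occurred is already defined in 5.3, but it has no stated bearing on the conclusion. If the role is left open until results are known, either population could be put forward.

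**Working it through.** **Inputs from the protocol.** 100 per arm; limit 15% (taken as ±15 percentage points); expected success 90% in both arms; power 0.8; type I error 0.05 (all section 5.1).

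**Assumptions not in the protocol.** True success of 90% against 75% by procedure received, so that the true difference equals the limit; a Wald confidence interval for the difference that must lie wholly within ±15 points; and the crossover rates.

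**The plan's own figure.** For equivalence by two one-sided tests, n = 2p(1−p)(z₁₋ₐ + z₁₋β/₂)² / limit².
- At 0.05 per side: 0.18 × (1.645 + 1.282)² / 0.0225 = 68.5, so 69.
- At 0.025 per side: 0.18 × (1.960 + 1.282)² / 0.0225 = 84.1, so 85. With a continuity correction, 97.

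The stated 100 is therefore close to the continuity-corrected result at 0.025 per side, although the protocol does not name its variant. Exact power at 100 per arm with no exclusions is 88% with a 95% interval and 94% with a 90% interval.

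**Step 1: dilution under intention-to-treat.** If a fraction c of each arm receives the other procedure, the expected difference is 15 × (1 − 2c) points. If only one arm crosses, it is 15 × (1 − c).

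**Step 2: chance of false equivalence, intention-to-treat only.** This is the sum of the binomial probabilities of all outcomes whose interval lies within ±15 points.

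| Two-way crossover | Expected difference | 95% interval | 90% interval |
|---|---|---|---|
| 0% | 15.0 | 2.7% | 5.4% |
| 2% | 14.4 | 3.5% | 6.8% |
| 5% | 13.5 | 5.0% | 9.2% |
| 10% | 12.0 | 8.5% | 14.7% |

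One-way crossover of 2, 5 or 10% gives about 3.1, 3.7 or 5.0% with a 95% interval, and 6.0, 7.1 or 9.2% with a 90% interval (averages of the two directions).

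**Step 3: requiring both populations to agree (simulation, 1,000,000 runs).** If crossover is unrelated to prognosis, false equivalence over 0 to 10% two-way crossover stays at 2.6 to 2.7% (95% interval) or 5.2 to 5.4% (90% interval).

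**Step 4: crossover related to prognosis.** As an illustration, let 10% of the mucopexy-alone arm be patients with 50% success who receive the Doppler procedure instead, with the arm mean before crossover kept at 75%. The uncrossed remainder then succeeds at (0.75 − 0.10 × 0.50) / 0.90 = 77.8%, so excluding the crossers makes that arm look better.
- Crossers succeed 65% of the time: intention-to-treat 5.1% against both sets 4.6% (95% interval); 9.4% against 8.6% (90% interval).
- Crossers succeed 80% of the time: 9.0% against 6.9%; 15.4% against 12.1%.
- Protocol-compliant set alone: 14.0% (90% interval).

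**Step 5: cost in power.** With true success of 90% in both arms and random exclusions of 5, 10, 15 or 20%, the chance that both sets pass is about 84, 81, 78 or 75% (95% interval), or 92, 90, 88 or 85% (90% interval).

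**The case against.** The other side has four serious arguments.

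- **This is the business of the statistical analysis plan.** Which population supports the primary one is often settled there, and no such plan was available for this review. That limits the point but does not remove it. Section 5.3 is not silent: it fixes one basis of analysis and defines a second population without a use. If a separate plan gives it a role, the protocol text still needs to match.
- **Crossover may be rare.** The treatment is a single operation, section 3.5 says "All surgeons must have prior experience in the treatment of hemorrhoids with DGHAL and mucopexy", and section 3.7.2 excludes patients with a clear preference. This stands. At 2% the effect is small, and nothing in the protocol supports 10% in each arm.
- **With a 95% interval the error stays at about 5% or less for two-way crossover up to 5%.** This stands too, and the stated sample size fits that interval better than a 90% one. Even so, the error nearly doubles from its starting value of 2.7%.
- **The confidence-interval rule is itself an assumption.** Section 5.2 names only a Chi-square test for categorical outcomes. That is a separate and larger gap: reading equivalence from a non-significant uncorrected Chi-square would give about 18% false equivalence at 90% against 75% with no crossover at all. The population question is secondary to it.

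A reader might infer that intention-to-treat is the wrong analysis here and that the protocol-compliant set should replace it. The documents do not support that. Intention-to-treat is a valid primary basis, and in the prognosis-related example the compliant set alone is also biased towards equivalence. Nor does section 5.3 discard the compliant set: it is to be reported, but without an inferential role.

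**Conclusion.** The point holds as a weakness in a stated choice that should be corrected. In a declared equivalence trial, the only stated analysis leans towards the trial's claim whenever patients cross over, and the population that could check this has no part in the conclusion. The direction of the bias does not depend on the crossover rate as long as crossover merely mixes the two procedures; its size does. Under the assumptions above, false equivalence rises from 2.7% to between 3.5 and 8.5% with a 95% interval, or from 5.4% to between 6.8 and 14.7% with a 90% interval, for two-way crossover of 2 to 10%.

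Two stronger readings should be resisted. The protocol does not show that this trial will have an error rate of 9 to 15%: those values need a 90% interval with appreciable crossover, or (for about 9% with a 95% interval) 10% prognosis-related crossover in which the crossers do well. Nor would agreement between populations guarantee error control: it holds the error near nominal only if crossover and exclusions are unrelated to prognosis, and otherwise reduces the inflation without removing it. Confidence is moderate, because the crossover rate and the interval rule are both assumed.

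**What to change.** Keep intention-to-treat as the primary analysis and add to section 5.3 wording such as: *The 1-year recurrence difference and its confidence interval will be repeated in the protocol-compliant population. Crossovers will be reported by arm. Equivalence will be claimed as robust only if both populations support it against the 15-point limit; any disagreement will be reported as such.* State in the same section what processing a patient must have received to count as compliant, so that the set can be formed.

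Separately, section 4.2 gives group B Doppler-guided ligation without mucopexy, whereas sections 3.1, 3.2.1 and 4.2.1.3 describe a comparison arm that has mucopexy without Doppler guidance. These passages contradict each other and must be reconciled before anyone can be classified as compliant.

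The cost is a few sentences, one definition and one repeat analysis in a population already defined. If agreement is required, some power is lost: with a 95% interval it falls below the planned 80% at about 15% exclusions. The protocol-compliant set can itself be biased when exclusions relate to prognosis, so it supplements intention-to-treat and does not replace it.

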3.2.2 Secondary

- SAFETY: Demonstration that the new treatment will not add related morbidity
- Comparison of the outcome among the two devices (THD and AMI/ HAL-RAR) for DGHAL

_

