3.6.1 Definition of Adverse Events

- Urinary retention will be defined as the condition of urinary dysfunction that occurs following surgery and requires intervention, including placement of urinary catheter.
- Pyrexia will be defined as any documented patient temperatures >38.0 C that require any treatment intervention such as antipyretics or that result in an increase in hospital stay.
- Surgical site infection purulent discharge from the wound with positive culture
- Post operative bleeding requiring reintervention, or balloon tamponade of the anal mucosa or transfusion within 1 month from the operation

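### Section 5.3 analyses all data by original allocation without exempting morbidity; a comparison by procedure performed should stand beside it

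*Protocol*

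**What the plan says.** Protocol section 5.3 gives one general rule: "Data analysis will be performed in accordance with the intention to treat principle". It continues: "If a violation of randomization occurs, all patients will be analyzed according to the original allocation". Neither sentence is limited to recurrence or to efficacy, and neither mentions safety.

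The same section lists two populations under the words "The following information will be prospectively collected and reported":

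- The all-randomized population: "Any subject randomized into the study, regardless of whether they receive the intervention".
- The protocol-compliant population: "Any subject who was randomized and received both the study intervention and received the required protocol processing".

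Neither population is assigned to an endpoint.

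Section 3.2.2 lists as a secondary endpoint "SAFETY: Demonstration that the new treatment will not add related morbidity". The adverse events in section 3.6.1 follow from the operation. Post-operative bleeding, for example, counts when it is an event "requiring reintervention, or balloon tamponade of the anal mucosa or transfusion within 1 month from the operation". For categorical outcomes section 5 prescribes a "Chi-square test for categorical variables", two-sided at 0.05. The only margin given, 15%, belongs to the primary endpoint.

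**The concern.** The by-allocation rule suits the randomised comparison of recurrence. It fits less well with a question about complications caused by an operation. Read as written, a patient allocated to mucopexy alone who receives Doppler-guided ligation and then bleeds is counted under mucopexy alone, and the reverse also holds. A patient who is never operated on stays in the denominator of the all-randomized set but cannot have an operative complication.

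When such deviations are balanced and unrelated to outcome, they pull the two morbidity rates together. In a comparison meant to find a difference, that is conservative. Where the aim is to show that nothing is added, it is not: a real excess with mucopexy alone would look smaller and be less likely to reach significance. Neither population in section 5.3 groups operated patients by the procedure they received, so the planned tables could not show that this had happened.

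**Working it through.** **Inputs.** The Protocol supplies the by-allocation rule and the two populations (5.3), 100 patients per arm (5.1) and a two-sided test at 0.05 (5.2). It states no morbidity, switching or non-operation rate, so there is no safety figure to reproduce. All rates below are assumptions.

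**Formula.** Let p1 be the true morbidity rate of the procedure with more complications and p2 that of the other. In each arm a fraction s receives the other procedure and a fraction u is never operated on and has no operative event. Deviations are equal in both arms and unrelated to outcome. By allocation:

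- Arm 1: (1 - u - s) × p1 + s × p2
- Arm 2: (1 - u - s) × p2 + s × p1
- Difference: (1 - u - 2s) × (p1 - p2)

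**Assumed 10% vs 5%, true difference 5 points.**

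- u = 2%, s = 3%: 9.5 + 0.15 = 9.65% vs 4.75 + 0.30 = 5.05%. Difference 4.6 points, 8% understated.
- u = 5%, s = 10%: 8.5 + 0.5 = 9.0% vs 4.25 + 1.0 = 5.25%. Difference 3.75 points, 25% understated.

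**Assumed 20% vs 10%, true difference 10 points, 100 per arm.**

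| s | u | Rates by allocation | Difference | Power |
|---|---|---|---|---|
| 0 | 0 | 20.0% vs 10.0% | 10.0 points | 0.51 |
| 5% | 5% | 18.5% vs 10.0% | 8.5 points | 0.40 |
| 10% | 10% | 17.0% vs 10.0% | 7.0 points | 0.30 |

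**What the protocol-compliant set changes.** It takes never-operated patients out. Its wording does not settle what happens to switched patients.

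- If they stay in their allocated arm, the factor becomes (1 - u - 2s)/(1 - u). At u = 5%, s = 10% this is 0.75/0.95 = 0.79, or about 3.9 points instead of 5.
- If they are dropped as non-compliant, the difference is restored under these assumptions, but their complications are not counted in that set under either procedure.

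**Where the direction reverses.**

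- Unequal non-operation: the true rate is 10% in both arms and 10% of the Doppler arm alone is never operated on. By allocation the Doppler arm shows 0.9 × 10% = 9% against 10% for mucopexy alone. This counts against the new treatment.
- Selective conversion: complications by allocation are 10/100 (Doppler) and 15/100 (mucopexy alone), and five complicated mucopexy-alone cases were converted to Doppler-guided ligation. By procedure performed the counts are 15/105 = 14.3% (Doppler) and 10/95 = 10.5% (mucopexy alone). Here the as-treated count flatters the new treatment.

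**The case against.** **This is an omission that the statistical analysis plan may fill.** Section 5.3 never names safety, and the population for adverse events is often set in the analysis plan, which is not at hand. It is true that safety is covered only by inference from the unqualified wording. But section 5.3 is not silent: it states a rule for data analysis and for all patients, and morbidity is a listed endpoint. An analysis plan that simply followed this text would carry the problem over.

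**The protocol-compliant set already deals with dilution.** This stands for never-operated patients. It does not stand for switched patients, and the set is not linked to adverse events.

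**By-allocation safety analysis is legitimate.** It asks whether choosing mucopexy alone adds morbidity, and it keeps the protection of randomisation. This stands. A reader might infer that the allocation rule is simply wrong for safety and that an as-treated analysis should replace it. The selective-conversion example shows why that goes too far.

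**The effect is small and switching is unlikely.** Section 3.7.2 excludes patients with a clear preference, and section 3.5 requires surgeons experienced in Doppler-guided ligation and mucopexy. At 10% vs 5% with 100 per arm, the standard error of the difference is √(0.10 × 0.90/100 + 0.05 × 0.95/100) = 3.7 points. The shifts of 0.4 and 1.25 points are therefore about 0.1 and 0.3 standard errors. This limits the importance of the point but does not remove it.

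**The monitoring board sees the clinical forms (6.3).** That protects patients during the trial. It does not determine the final morbidity comparison.

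**Conclusion.** The point holds in a limited form. Section 5.3 applies grouping by allocation to all data analysis, does not exempt morbidity, and defines no set of operated patients grouped by procedure performed. Under balanced, non-selective deviations the morbidity difference shrinks by the factor (1 - u - 2s): 8% to 25% in the 10% vs 5% illustrations, and 15% to 30% in the 20% vs 10% ones. All of these rest on assumed rates.

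A reader might infer that the plan is biased towards finding no added morbidity. The documents do not support that as a general statement: the direction depends on how deviations fall between the arms and on whether they relate to outcome, and the Protocol gives no information on either. Nor do they support the reading that never-operated patients dilute every planned analysis, since the protocol-compliant set leaves them out. The stated sample size and the primary comparison are unaffected. This is an inexpensive improvement to the safety analysis.

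**What to change.** Keep the by-allocation comparison and add to section 5.3:

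> Adverse events (3.6.1) will also be analysed in all patients who were operated on, grouped by the procedure actually performed; both analyses will be reported with equal prominence, and no added morbidity will be concluded only if they agree.

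Agreement should mean that the same criterion for no added morbidity is met in both analyses. The operative form should record whether Doppler-guided ligation was done. That form is not among the documents, so it may already do so.

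The cost is one sentence in section 5.3 and one field on a form, with no change to sample size or the primary analysis. The downside is that the comparison by procedure performed is not randomised and can be biased by selective conversion. This is why it is added beside the by-allocation result and does not replace it. A disagreement between the two would be a signal to examine and report the switched patients individually.

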6. ETHICS

6.1 Risks of Participation

Patients in both study arms will be informed of standard risks of hemorrhoid surgery, such as bleeding, surgical site infections, thrombotic complications, cardiac, or pulmonary complications.

6.2 Institutional Review Boards

This study will be conducted in accordance to the principles of the Declaration of Helsinki and good clinical practice guidelines. The study protocol will be approved by the Ethics committee of all

participating institutions. Prior to randomization, written informed consent will be obtained from all patients.

6.3 Data Safety Monitoring Committee

A data safety monitoring board (DSMB) will be established with experts independent of the authors. The chairman of the DSMB will receive the clinical data forms continuously from the coordinating center and will review data. The DSMB chair may at any time suggest to the Study Chair to terminate the study in case of ethical concerns such as unacceptable complication rates and others.

7. AUTHORSHIP AND PUBLICATION

The rules described herein apply to any presentation of this study. Members of the Protocol Writing Committee as well as Study Chairs qualify for authorship of this study. Vancouver Authorship Guidelines (for full document rules shall apply please full article http://www.icmje.org/index.html). Surgeons that include patients will attain authorship through a group authorship where names of surgeons will be mentioned. The order of the authors in the group authorship according their active contribution to the trial. The study results may only be published and/or presented as final analyses after the completion of the study and needs authorization by the study chairs. Publication and/or presentation are defined as any article, podium presentation, poster, abstract, or any other public presentation of this research. As is generally accepted, members of the DSMB should be independent and not involved in the study in any way including authorship.

8. SPONSORSHIP

The trial is not officially sponsored.

9. APPENDICES

Consent form

Form of words

